6.0 STATISTICAL ANALYSIS

6.1 Study Endpoints

6.1.1 Primary and Secondary Endpoints

The primary outcome is comparison of the MMRCDS and CDS severity scores at 8-week post-assessment between study arms, controlling for baseline values.

The secondary outcomes will be comparison of quality of life, anxiety, depression, and activity level between study groups. To assess quality of life, we will compare the post-assessment (8-week) FACT-L scores between study arms, controlling for baseline values. To evaluate anxiety and depression symptoms, we will similarly compare the continuous scores as well as rates of depression and anxiety symptoms reported per HADS score at 8 weeks between study arms, controlling for baseline values. To assess activity level, we will compare the percentage of time spent immobile but awake on actigraphy and self-report weekly leisure-time physical activity score at 8 weeks between study groups, controlling for baseline values.

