2.0 OBJECTIVES

2.1 Primary Aim

To demonstrate the efficacy of the brief behavioral intervention for improving self-reported dyspnea (primary outcome) in patients with advanced lung cancer

Hypothesis: Participants with advanced lung cancer who are randomly assigned to receive the brief behavioral intervention will report statistically and clinically significant improvements in dyspnea compared to those assigned to usual care.

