6.3 Analysis Plan

6.3.1 Aim 1

Aim 1: To demonstrate the efficacy of the brief behavioral intervention for improving dyspnea (primary outcome) in patients with advanced lung cancer.

Hypothesis 1: Participants with advanced lung cancer who are randomly assigned to receive the brief behavioral intervention will report statistically and clinically significant improvements in dyspnea (per self-report MMRCDS and CDS) compared to those assigned to usual care.

Analysis: Analyses will begin with descriptive and graphical summaries of the endpoints. As the MMRCDS is an ordinal measure, the statistical significance of between-group differences in the primary outcome will be assessed first with the Wilcoxon-Rank Sum test and then with generalized estimating equations (GEE), with appropriate covariates. The CDS is a continuous interval measure, and we will assess between-group differences in these scores using general linear models (GLM). All statistical tests will be two-sided with an alpha level of .05. For these primary outcomes, we will examine between-group differences (i.e., intervention versus control) in MMRCDS and CDS scores at the 8-week post-assessment, controlling for baseline values. In the event that the effect of the intervention differs by cancer type, use of opiate medication or other patient characteristic, we will examine these variables as interaction terms in the GEE and GLM analyses. We will also evaluate generalized linear mixed models of the longitudinal data, allowing us to

account for dependency among MMRCDS and CDS scores over time and to control for demographic and clinical factors, such as disease progression, (as necessary for any imbalances in baseline variables) when examining between-group differences in the MMRCDS and CDS scores across the multiple study time points (i.e., baseline, 8, 16, 24 weeks). Finally, we will compute the effect sizes and Reliability Change Index⁶⁸ to assess practical and clinical significance of the differences in the primary and secondary outcomes. The GLM model will generate an effect size estimate, which can also be calculated by hand ($d = \text{Mean}_{\text{change score CBT group}} - \text{Mean}_{\text{change score control group}} / \text{SD}_{\text{pooled}}$). Cohen⁶⁹ utilizes cutoffs of 0.2 for a small effect, 0.5 a medium effect, and 0.8 for a large effect.

6.3.2 Aim 2

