Aim 2: To demonstrate the efficacy of the brief behavioral intervention for improving quality of life, anxiety, depression, and activity level (secondary outcomes) in patients with advanced lung cancer.

Hypothesis 2: Participants with advanced lung cancer who are randomly assigned to receive the brief behavioral intervention will experience statistically and clinically significant improvements in quality of life (FACT-L), anxiety and depression (HADS), as well as activity level (per self-report Godin-Shephard Leisure-Time Physical Activity Questionnaire and the percentage of time spent immobile but awake on actigraphy) compared to those assigned to usual care.

Analyses: The statistical significance of between-group differences for the continuous secondary outcomes will be assessed with general linear models (GLM) and linear mixed models, with appropriate covariates and an alpha level of .05. We will examine the between-group differences (i.e., intervention versus control) at 8-week post-assessment for each specific secondary outcome (all are continuous variables), controlling for baseline values. In the event that the effect of the intervention differs by cancer type, use of opiate medication or other patient characteristic, we will examine these variables as interaction terms in the GLM analysis. We will explore independent improvements in these secondary outcomes by adding changes in MMRCDS or CDS severity scores as a covariate. Finally, we will also again estimate practical and clinical significance of these outcomes (using Cohen's d and Reliability Change Index) and conduct linear mixed models to examine the trajectory of between-group differences in these variables across all study time points.

6.3.3 Aim 3

Aim 3: To explore mediators and moderators of the effect of the brief behavioral intervention on patient-reported outcomes.

Hypothesis 3: Intervention effects on patient-reported dyspnea will be mediated by improved mastery in managing breathlessness and potentially moderated by patient demographic and clinical factors (e.g., gender, age, opioid use, performance status, and disease comorbidity).

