Analyses: We will conduct bootstrapped tests of mediation to determine whether group differences in self-reported dyspnea (outcomes: MMRCDS and CDS) are mediated by improved mastery in managing the symptom (mediator: CRQ). Finally, we will create interaction terms for the GEE analyses and linear mixed models to examine whether differences in reported dyspnea are moderated by patient factors (e.g., gender, age, opioid use, etc.).

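### MMRCDS and CDS are both primary at two-sided .05 with no rule for a split result; if one scale is taken as enough, familywise error is about 7%-10%, and if both are required, the 80% power is per outcome only

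*Combined protocol and SAP*

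**What the plan says.** Section 6.1.1 (Primary and Secondary Endpoints) puts two scales into one primary outcome: "The primary outcome is comparison of the MMRCDS and CDS severity scores at 8-week post-assessment between study arms, controlling for baseline values". Section 6.3.1 (Aim 1) refers to them in the plural: "For these primary outcomes, we will examine between-group differences (i.e., intervention versus control) in MMRCDS and CDS scores at the 8-week post-assessment". The same section sets the level for every test: "All statistical tests will be two-sided with an alpha level of .05".

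CDS is analysed with a general linear model. For MMRCDS, two tests are named, and significance "will be assessed first with the Wilcoxon-Rank Sum test and then with generalized estimating equations (GEE), with appropriate covariates".

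Hypothesis 1 in section 6.3.1 speaks of "improvements in dyspnea (per self-report MMRCDS and CDS) compared to those assigned to usual care". The hypothesis in section 2.1 names no scale; it says participants "will report statistically and clinically significant improvements in dyspnea compared to those assigned to usual care". Section 6.2 states 80% power for a difference of 0.40 SD with 200 completers at two-sided 0.05.

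Nothing in section 6 splits the alpha, orders the two scales, or says what a result on only one of them would mean. The success benchmarks in section 6.5 concern FACT-L and the Reliability Change Index and do not settle it. Section 5.5.1 also counts HADS and FACT-L among the primary outcome assessments when it describes the abbreviated questionnaire, whereas section 6.1.1 makes them secondary.

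**The concern.** Aim 1 is the trial's efficacy claim, and it concerns dyspnea in general. With two primary scales and an unadjusted .05 for each, three outcomes are possible: both significant, neither, or one. The plan gives no agreed meaning to the third.

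If the rule is chosen after the results are known, a single significant scale can be presented as success at an error rate above the nominal level. If both were always meant to be required, the error is controlled, but the stated 80% is not the chance of meeting Aim 1.

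A split result is quite possible. MMRCDS is one item with five grades, while CDS has twelve items covering several dimensions. Entry also requires an MMRCDS score of at least 2, which restricts the baseline range on that scale only.

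The two tests named for MMRCDS leave a second choice open, because the plan does not say which one decides.

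**Working it through.** **Inputs.** Two primary scales (6.1.1); two-sided .05 for each (6.3.1); 0.40 SD and 200 completers, taken as 100 per arm (6.2; 1:1 allocation in 5.5). The correlation ρ between the two test statistics is not in the documents, so it is an assumption and is shown as a range.

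**Step 1: the plan's own figure.** The expected test statistic is 0.40/√(2/100) = 2.828. Power for one outcome is Φ(2.828 − 1.960) = Φ(0.868) = 80.7% (80.4% with the t distribution). The number needed for 80% is 2(1.960 + 0.842)²/0.40², which gives 99 per arm, or 198 in total. Section 6.2 is reproduced as power for a single outcome.

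**Step 2: one scale taken as enough.** With no true effect on either scale and ρ = 0, the two-sided familywise error is 1 − 0.95² = 9.75%. The chance of a false claim favouring the intervention is 1 − 0.975² = 4.94%. For other ρ, I used the bivariate normal probabilities P(|Z₁| > 1.96 or |Z₂| > 1.96) and P(Z₁ > 1.96 or Z₂ > 1.96).

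| ρ | Two-sided familywise error | False claim favouring intervention |
|---|---|---|
| 0 | 9.75% | 4.9% |
| 0.3 | 9.5% | 4.8% |
| 0.5 | 9.1% | 4.5% |
| 0.7 | 8.3% | 4.2% |
| 0.8 | 7.8% | 3.9% |
| 0.9 | 7.0% | 3.5% |

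For a single test the corresponding values are 5% and 2.5%. Two self-reports of the same symptom should be positively correlated, so ρ near 0 is the least likely end. The table counts one test per scale. If either the Wilcoxon or the GEE result could count for MMRCDS, the error would be somewhat higher.

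**Step 3: both scales required.** A false claim then needs both tests to be significant, so error is at most 5%. Joint power is P(Z₁ > 1.96 and Z₂ > 1.96) with both means at 2.828. At ρ = 0 this is 0.807² = 65.2%. At ρ = 0.3, 0.5, 0.7 and 0.8 it is 67.7%, 69.7%, 72.2% and 73.8%.

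Baseline adjustment raises it. For continuous outcomes the expected statistic becomes 2.828/√(1 − b²), where b is the assumed baseline correlation and ρ is now the residual correlation. For ρ from 0 to 0.8, joint power is 71.0%-78.2% at b = 0.3 and 81.8%-86.2% at b = 0.5.

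**Step 4: how often the result splits.** At 0.40 SD on both scales, before adjustment, the chance that exactly one scale succeeds is P(at least one) − P(both):
- ρ = 0: 96.3% − 65.2% = 31%
- ρ = 0.5: 91.7% − 69.7% = 22%
- ρ = 0.8: 87.7% − 73.8% = 14%

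**Step 5: cost of controlling error when one scale may suffice.** A scale that succeeds alone must reach .025 (critical value 2.241). Power for a continuous outcome is Φ(2.828 − 2.241) = 72.1%. With b = 0.3 it is Φ(2.965 − 2.241) = 76.5%, and with b = 0.5 it is Φ(3.266 − 2.241) = 84.7%.

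**The case against.** The strongest reply is that the text leans towards both scales being required. Section 6.1.1 speaks of one primary outcome and joins the scales with 'and', as does Hypothesis 1. On that reading no error is inflated, and the power sentence is correct for each outcome. This stands as far as it goes. A reader might infer that the plan does run a 7%-10% error rate; the documents do not support that, because nowhere do they say that one scale is enough. Equally, naming two measures in a hypothesis does not say what follows if only one succeeds, so the gap remains.

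A reader might also take section 6.3.2, which explores secondary outcomes "by adding changes in MMRCDS or CDS severity scores as a covariate", as an either-scale rule. It is not one: it concerns a covariate. Section 6.3.3 merely lists the two scales as outcomes for the mediation analysis.

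On the MMRCDS tests, it is fair to say that baseline control in sections 6.1.1 and 6.3.1 points to the adjusted model. But the Wilcoxon test is listed first, and the plan does not say that it is only supportive.

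Lastly, section 5.5.1 could suggest four primary outcomes. It describes a shortened questionnaire, and section 6.1.1 is explicit that HADS and FACT-L are secondary. This is a wording conflict to reconcile, and the figures above do not depend on it.

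**Conclusion.** The concern holds as a missing decision rule on the primary claim. The error inflation is conditional on one scale being accepted, and its size depends on an assumed correlation of 0.9 down to 0.

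If both scales are required, what remains is labelling. The 65%-74% assumes 0.40 SD on each scale, 200 completers, correlation 0-0.8 and no baseline adjustment. A reader might infer that the 80% in section 6.2 is wrong or that the trial is underpowered. The documents do not support that: the figure reproduces per outcome, and the planned baseline adjustment could bring joint power to 80% or more if the baseline correlation is about 0.5.

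All the power figures treat both scales as continuous. Power for the five-level MMRCDS may be lower, depending on how week-8 scores spread over the levels. The documents do not give that distribution, so I put no figure on it. This should be fixed, and the trial remains fully analysable.

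**What to change.** Before unblinded data are seen, state in sections 6.1.1 and 6.3.1 that the week-8 baseline-adjusted models decide (GEE for MMRCDS, GLM for CDS) and that the unadjusted Wilcoxon test is supportive. Then adopt one of two options, which are equally acceptable:

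- **(a) Both required.** Aim 1 is met only if both scales are significant at two-sided .05. Label the 80% in section 6.2 as per-outcome power.
- **(b) Either may support the claim.** Apply Hochberg or Holm across the two scales at overall two-sided .05. Under Hochberg, if both scales are below .05, both are claimed; in a split result the significant scale must reach .025. Under Holm, the smaller p-value must reach .025 before the other is tested at .05.

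Also reconcile the list of primary outcome assessments in section 5.5.1 with section 6.1.1.

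The cost is wording only, with no change to data collection or sample size. Option (a) accepts the joint power shown above. Option (b) lowers power when only one scale responds, from about 81% to about 72% for a continuous outcome before baseline adjustment (about 77% or 85% at an assumed baseline correlation of 0.3 or 0.5), and possibly lower for MMRCDS.

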6.2 Sample Size and Power Calculation

Although we observed a large effect size for the brief behavioral intervention on patient-reported dyspnea in our previous trial (Cohen's $d=1.0$), we chose to be conservative in estimating the sample size to power the proposed RCT given the inclusion of usual care control group, proposed tests of mediation and moderation, and rate of attrition observed in our pilot trial (i.e., 16%). Therefore, if a total of 200 study participants complete this two-treatment parallel-design study, the probability is 80% that the study will detect a treatment difference in the primary and secondary outcomes at a two-sided 0.05 significance level (if the true difference between treatments is 0.40 times the standard deviation (i.e., the lower bound of a medium effect size).

6.3 Analysis Plan

6.3.1 Aim 1

Aim 1: To demonstrate the efficacy of the brief behavioral intervention for improving dyspnea (primary outcome) in patients with advanced lung cancer.

Hypothesis 1: Participants with advanced lung cancer who are randomly assigned to receive the brief behavioral intervention will report statistically and clinically significant improvements in dyspnea (per self-report MMRCDS and CDS) compared to those assigned to usual care.

Analysis: Analyses will begin with descriptive and graphical summaries of the endpoints. As the MMRCDS is an ordinal measure, the statistical significance of between-group differences in the primary outcome will be assessed first with the Wilcoxon-Rank Sum test and then with generalized estimating equations (GEE), with appropriate covariates. The CDS is a continuous interval measure, and we will assess between-group differences in these scores using general linear models (GLM). All statistical tests will be two-sided with an alpha level of .05. For these primary outcomes, we will examine between-group differences (i.e., intervention versus control) in MMRCDS and CDS scores at the 8-week post-assessment, controlling for baseline values. In the event that the effect of the intervention differs by cancer type, use of opiate medication or other patient characteristic, we will examine these variables as interaction terms in the GEE and GLM analyses. We will also evaluate generalized linear mixed models of the longitudinal data, allowing us to

account for dependency among MMRCDS and CDS scores over time and to control for demographic and clinical factors, such as disease progression, (as necessary for any imbalances in baseline variables) when examining between-group differences in the MMRCDS and CDS scores across the multiple study time points (i.e., baseline, 8, 16, 24 weeks). Finally, we will compute the effect sizes and Reliability Change Index⁶⁸ to assess practical and clinical significance of the differences in the primary and secondary outcomes. The GLM model will generate an effect size estimate, which can also be calculated by hand ($d = \text{Mean}_{\text{change score CBT group}} - \text{Mean}_{\text{change score control group}} / \text{SD}_{\text{pooled}}$). Cohen⁶⁹ utilizes cutoffs of 0.2 for a small effect, 0.5 a medium effect, and 0.8 for a large effect.

6.3.2 Aim 2

Aim 2: To demonstrate the efficacy of the brief behavioral intervention for improving quality of life, anxiety, depression, and activity level (secondary outcomes) in patients with advanced lung cancer.

Hypothesis 2: Participants with advanced lung cancer who are randomly assigned to receive the brief behavioral intervention will experience statistically and clinically significant improvements in quality of life (FACT-L), anxiety and depression (HADS), as well as activity level (per self-report Godin-Shephard Leisure-Time Physical Activity Questionnaire and the percentage of time spent immobile but awake on actigraphy) compared to those assigned to usual care.

Analyses: The statistical significance of between-group differences for the continuous secondary outcomes will be assessed with general linear models (GLM) and linear mixed models, with appropriate covariates and an alpha level of .05. We will examine the between-group differences (i.e., intervention versus control) at 8-week post-assessment for each specific secondary outcome (all are continuous variables), controlling for baseline values. In the event that the effect of the intervention differs by cancer type, use of opiate medication or other patient characteristic, we will examine these variables as interaction terms in the GLM analysis. We will explore independent improvements in these secondary outcomes by adding changes in MMRCDS or CDS severity scores as a covariate. Finally, we will also again estimate practical and clinical significance of these outcomes (using Cohen's d and Reliability Change Index) and conduct linear mixed models to examine the trajectory of between-group differences in these variables across all study time points.

6.3.3 Aim 3

Aim 3: To explore mediators and moderators of the effect of the brief behavioral intervention on patient-reported outcomes.

Hypothesis 3: Intervention effects on patient-reported dyspnea will be mediated by improved mastery in managing breathlessness and potentially moderated by patient demographic and clinical factors (e.g., gender, age, opioid use, performance status, and disease comorbidity).

Analyses: We will conduct bootstrapped tests of mediation to determine whether group differences in self-reported dyspnea (outcomes: MMRCDS and CDS) are mediated by improved mastery in managing the symptom (mediator: CRQ). Finally, we will create interaction terms for the GEE analyses and linear mixed models to examine whether differences in reported dyspnea are moderated by patient factors (e.g., gender, age, opioid use, etc.).

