5.3.3 Usual Care

Patients in both study groups may receive any usual care for their dyspnea as deemed appropriate by their clinicians. Cancer care clinicians commonly prescribe opioids, benzodiazepines and nasal canula oxygen for patients with dyspnea, though these interventions tend to have minimal benefit. In addition, some patients may undergo procedures for pulmonary complications that can impact their respiratory status, including draining pleural effusions and stent placement or radiation therapy for bronchial obstructions. MGH and DFCI Pulmonology clinicians will provide consultative guidance for the investigative team on such cases in the study, regardless of group assignment. While the study staff will track medical therapies and procedures through the electronic health record for patients in both study groups, participation in this study will not impact use of these modalities. We do not anticipate the study groups to differ significantly in their use of medical therapies, though these factors will serve as control variables in the final analyses as necessary.

After completion of the final study follow-up, patients randomized to receive usual care will be offered the study intervention materials to be delivered either in person, via mail or email. They will also be offered the opportunity to meet with a study clinician in person, by phone, or via secure video to review the materials and ask questions. At the time of

enrollment, patients will be made aware that these resources will be available upon completion of the final study assessment.

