5.4 Data Collection Procedures

5.4.1 Timing of Data Collection

The following table depicts the assessments, measures and time points for the proposed data collection.

	Screening	Baseline	Weeks 8, 16, 24	Post Study
Chart review for eligibility and baseline clinical characteristics	X			
Modified Medical Research Council Dyspnea Scale (MMRCDS)	X	X	X	
Cancer Dyspnoea Scale (CDS)		X	X	
Demographic Questionnaire		X		
Functional Assessment of Cancer Therapy-Lung (FACT-L)		X	X	
Hospital Anxiety and Depression Scale (HADS)		X	X	
Godin-Shephard Leisure Time Physical Activity Questionnaire (GSLTPAQ)		X	X	
Chronic Respiratory Disease Questionnaire (CRQ)		X	X	
Self-report ECOG Performance Status		X	X	
Actigraph and activity log (for 3 days)		X	X (week 8 only)	
Chart review for treatment, medical orders, service utilization				X

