5.4.2 Data from the Electronic Health Record

Clinical information regarding tumor type (NSCLC, SCLC, mesothelioma), date of diagnosis of advanced disease, previous cancer therapies, current treatment regimen, and performance status will be collected at baseline. The post study review of the electronic health record (EHR) will include information on disease progression, any changes in cancer treatment, and number of emergency department (ED) visits and hospitalizations during the study period.

Medical comorbidity will be assessed at the time of baseline data collection with the Charlson Comorbidity Index (CCI).⁶⁷ We will review health records for the presence of (1) pulmonary, cardiac, hepatic, and renal disease, (2) current and other malignancies, and (3) other morbidities (diabetes, cerebrovascular disease, and rheumatologic conditions) and assign the appropriate CCI score.

Medical orders: We will collect data on medications to alleviate dyspnea (e.g., opioid analgesics), supplemental oxygen, and procedures for managing pleural effusions or bronchial obstruction.

[name] (Co-I), a thoracic oncologist, will oversee the collection of clinical information from the EHR as well as the review of medical scans to determine whether participants'

disease progressed during the study period.

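### The covariate rules let on-study therapies (and, in the longitudinal models, disease progression) act as controls for the dyspnea effect, and do not state the randomization strata as model terms

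*Combined protocol and SAP*

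**What the plan says.** **Primary comparison.** Sections 6.1.1 and 6.3.1 define it as MMRCDS and CDS at week 8 between arms, adjusted for the baseline score. For MMRCDS, Section 6.3.1 says the difference "will be assessed first with the Wilcoxon-Rank Sum test and then with generalized estimating equations (GEE), with appropriate covariates". CDS is analysed with a general linear model. The covariates are not listed.

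**Dyspnea therapies and procedures.** Section 5.3.3 has staff track these in the health record in both groups during the study. On their role in the analysis it says "though these factors will serve as control variables in the final analyses as necessary". The expectation given alongside that rule is "We do not anticipate the study groups to differ significantly in their use of medical therapies".

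**Disease progression.** The longitudinal mixed models in Section 6.3.1 are meant "to control for demographic and clinical factors, such as disease progression, (as necessary for any imbalances in baseline variables". Section 5.4.2, however, says "The post study review of the electronic health record (EHR) will include information on disease progression".

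**Opioid use.** It is a possible interaction term in Sections 6.3.1 and 6.3.2 and a moderator in Section 6.3.3. The baseline items in Section 5.4.2 end with "current treatment regimen, and performance status will be collected at baseline" and do not name it. The separate item "Medical orders: We will collect data on medications to alleviate dyspnea (e.g., opioid analgesics), supplemental oxygen, and procedures" carries no time point. The schedule in Section 5.4.1 puts "Chart review for treatment, medical orders, service utilization" in the post-study column.

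**Strata.** Section 4.3 stratifies by cancer type (three levels) and site (two levels). Section 6.3 never names site, and names cancer type only as an interaction term to be examined if the effect appears to differ by it.

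**The concern.** Randomization protects the comparison of arms on the outcome. It does not protect a comparison made conditional on something that happens afterwards. If patients who learn breathing techniques come to need fewer opioid or oxygen orders, adjusting for those orders removes part of the effect. If the sessions prompt more requests for treatment, adjusting enlarges it. The likeliest trigger for the discretionary rule in Section 5.3.3 is a visible arm difference, which is exactly when the adjustment does harm. The rule refers to the final analyses without limit, so it can reach the week-8 models.

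The progression clause is at odds with the plan's own schedule: a variable taken from the post-study review cannot be a baseline imbalance.

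The strata raise a smaller issue. With the covariate list undefined, whether site and cancer type enter could be settled after the data are seen. Leaving them out costs a little precision and, under blocked randomization, makes the test somewhat conservative.

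**Working it through.** **1. The plan's own power (Section 6.2).** Inputs: 200 completers (100 per arm), 0.40 SD, two-sided 0.05. SE = sqrt(2/100) = 0.1414; 0.40/0.1414 = 2.83; power = Φ(2.83 - 1.96) = 0.807. The stated 80% reproduces. With the planned baseline adjustment and an assumed correlation of 0.5, SE = 0.1414 × sqrt(0.75) = 0.1225 and power is Φ(3.27 - 1.96) = 0.904. These two figures are the comparators below, because they describe the analysis without on-study orders.

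**2. Size of the shift.** Adjusted effect = true effect - (slope of outcome on the covariate) × (arm difference in the covariate). All inputs here are assumed; the documents give none.

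- Orders 10 points apart, users 0.5 SD worse: shift 0.10 × 0.5 = 0.05, so -0.40 becomes -0.35 (intervention arm has fewer orders) or -0.45 (more).
- Orders 15 points apart, users 0.8 SD worse: shift 0.15 × 0.8 = 0.12, so -0.28 or -0.52.
- No arm difference: shift 0, estimate stays at -0.40.

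**3. Power and null rejection, 10-point case with fewer orders** (40% against 30%).

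- Mean within-arm variance of the order indicator: (0.24 + 0.21)/2 = 0.225.
- Outcome variance explained by orders: 0.5² × 0.225 = 0.056.
- Collinearity of arm with orders: R² = 0.25 × 0.10² / (0.225 + 0.0025) = 0.011.
- Without baseline: SE = sqrt(0.944 × 0.02 / 0.989) = 0.138. Power = Φ(0.35/0.138 - 1.96) = 0.72. With no true effect, the 0.05 shift gives rejection Φ(-1.60) + Φ(-2.32) = 0.065.
- With baseline correlation 0.5: residual variance 0.75 - 0.056 = 0.694, SE = 0.118, power 0.84, null rejection 0.07.

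Simulation gives about 71% and 83% power, and null rejection of about 0.06-0.07. The loss is therefore about 81% to 71%, or about 90% to 83%.

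**4. The 15-point, 0.8 SD case.** By the same formulas SE is about 0.13 without baseline and 0.11 with it. Null rejection is about 0.15 and 0.19; simulations run from 0.14 to 0.20.

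**5. Strata.** Assumed: sites 65/35, NSCLC 80% against 20% other. With both factors differing by d SD, the share of variance is 0.65 × 0.35 × d² + 0.80 × 0.20 × d² = 0.3875 d². That is 1.6%, 3.5% and 9.7% for d = 0.2, 0.3 and 0.5, so 0%-10% is the likelier range. Simulated power of the week-8 baseline-adjusted GEE (200 patients, five grades, baseline grade 2 or above, assumed blocks of 4, identity link), without and then with strata, at observed baseline correlations 0.15 / 0.26 / 0.41:

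| Strata share of variance left after baseline | Standard sandwich SE | Small-sample-corrected SE |
|---|---|---|
| 0% | .814→.817 / .838→.840 / .875→.878 | .801→.797 / .826→.821 / .865→.862 |
| 5% | .818→.835 / .841→.855 / .872→.885 | .806→.814 / .830→.837 / .863→.869 |
| 10% | .820→.848 / .853→.875 / .890→.909 | .808→.832 / .842→.860 / .882→.897 |

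Defining the 0.40 SD on the underlying continuous scale gives gains of up to 3.5 points at 10% (.766→.801). The range is thus about 0 to 4 points, or -0.5 to 2.4 with the corrected standard error.

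**The case against.** The best defence is that the plan expects no harm. Section 5.3.3 anticipates no significant difference in therapies and says participation will not affect their use. Section 6.5 sets the aim as an effect beyond usual care, which may be why therapies were listed as controls. Two sessions of 30-45 minutes may well leave prescribing unchanged. This stands as an argument about likelihood: with equal use there is no distortion. It does not justify the rule, because with equal use there is also no imbalance to correct, and randomization already gives both arms usual care.

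Several stronger readings are tempting and not supported:

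- **That progression enters the primary test.** It is named only for the supporting longitudinal models, and an arm effect on progression is unlikely.
- **That opioid use is defined after randomization.** The schedule says when charts are abstracted, not which order dates count. The use is ambiguous, and the moderator analysis is exploratory.
- **That the strata are excluded, or that omitting them biases the result.** The undefined covariate phrase does not exclude them, and omission causes no bias. The conservatism depends on blocking, which Section 4.3 does not state.
- **That MMRCDS has two competing primary tests.** If a win on either test counted, type I error would be about 6.4%-8.5% in simulation (assumed baseline correlations 0.3-0.7). The plan does not say either may count, and its baseline-adjusted definition of the endpoint points to the GEE.

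**Conclusion.** The concern holds for on-study therapies and procedures: as written, they may be used as controls in the primary week-8 models. For disease progression it holds in the supporting models, where the text contradicts the data schedule. The distortion can go either way, so it cannot be dismissed as conservative.

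The sizes rest on assumed arm differences and slopes. The 10-point example moves the estimate by 0.05 SD and costs about 7-10 power points where it shrinks. The 15-point example moves it by 0.12 SD. A reader might extend this to a halving of the effect to -0.20 SD. That would need a slope of 0.5 together with a 0.4 SD arm shift, about 20 points for an order given to 40% (0.4 × sqrt(0.24) = 0.196), and nothing in the documents suggests a difference that large.

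The strata point is secondary: small in power, with prespecification as the main reason to act. The baseline adjustment already planned is sound, and the stated sample size calculation reproduces. The plan should be corrected, but nothing here shows the trial's result to be invalid.

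**What to change.** - **Sections 5.3.3 and 6.3.1:** take on-study therapies, procedures and disease progression out of the efficacy models. Report them by arm and use them in labelled sensitivity analyses or as imputation auxiliaries.
- **Sections 6.3.1 and 6.3.2:** replace the open covariate wording with a fixed list of pre-randomization variables. The adjustment of secondary outcomes for change in dyspnea is already described as exploration and can stay so labelled.
- **Strata:** add cancer type and site as main effects to the week-8 GEE and GLM and to the longitudinal models, pooling SCLC and mesothelioma if sparse.
- **Deciding test:** state that MMRCDS is decided by the two-sided test of the arm term in the week-8 baseline-adjusted GEE, with a named link suited to an ordinal scale. State that the rank-sum test, which cannot adjust for baseline, is supportive.
- **Opioid use:** for interaction and moderator terms, define it from orders active before randomization.

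The cost is SAP wording plus abstraction of pre-randomization opioid orders within the chart review already planned. If the strata turn out not to be prognostic, up to about 0.5 power points may be lost with a small-sample-corrected standard error. No extra patients or visits are needed.
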